* We expect approximately 50% of these subjects will be tested negative for SCA1 and SCA3, and they will serve as controls. If we do not have 30 control subjects, we will recruit additional asymptomatic subjects who are of either sex aged 18 to 65 with neither SCA1 nor SCA3 mutations to serve as additional controls. Exclusion criteria described above also applies to control subjects.

Introduction

Background and study rationale

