We will enroll a subset of the prospectively enrolled 200 subjects in Aim 1. These subjects will consist of 30 (20 premanifest and 10 early-phase) subjects with the SCA1 mutation, 40 (27 premanifest and 13 early-phase) subjects with the SCA3 mutation and 30 controls (drawn from at-risk subjects who test negative for SCA1 or

SCA3 gene mutations and from spouses and other relatives who do not have symptoms, signs or risks of ataxia). We will enrich the SCA1 and SCA3 cohorts by inviting participants with a predicted time to ataxia onset within 10 years, based on their CAG repeat length and current age. For premanifest carriers and participants who are 50%-at-risk, we will target an age range of 27-50 years to minimize the probability of including participants too far from disease onset and those who are highly unlikely to have an expansion of CAG repeats in SCA1 or SCA3.

Study duration:

Participants will be scanned (within ± 2 weeks of the clinical study visit) at baseline, 6 month, 12 month, 24 month and 36 month time points during the READISCA study period. All MR visits will include completion of SARA exam prior to MR scan. Three additional time points may be included in the MR sub study to incorporate scans at 6 months, 18 months and 36 months.

Inclusion and exclusion criteria:

Inclusion criteria for Aim 2 will be the same as those in **Aim 1** and willingness to undergo MR procedures.

Exclusion criteria for Aim 2 will be the same as those in **Aim 1** and inability to undergo MRI scanning (claustrophobia, presence of paramagnetic substances or pacemakers in body, weight over 300 lbs.), pregnancy or lactation in women of childbearing potential not protected by an effective means of contraception, and other neurological diseases than those of interest. In addition, potential study participants will be excluded from the study if any of the following criteria are present at any point in the study: structural abnormalities such as subdural hematoma, primary or metastatic intracranial neoplasms, and concurrent illnesses or treatments interfering with cognitive function, such as a stroke or normal pressure hydrocephalus.

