At any time during the study, the participant may revoke authorization to use data and/or samples. However, the sponsor and the study investigator can still keep and use any information that is already received to the extent necessary to preserve the integrity of the research study.

Sample Size Justification

For Aim 1 study of prospective data collection the sample size is guided by feasibility (regarding our realistic ability to enroll premanifest and very early stage subjects across US and Europe), rather than power. The sample size of 200 participants will ensure enrollment of >60 participants with SCA1 and >100 participants with SCA3, which should provide sufficient power at least equivalent to the previous US and EUROSCA studies.

For Aim 2 the sample size is determined based on the RISCA study, which included imaging data from 26 SCA1 mutation carriers and 9 SCA3 mutation carriers and reported significant VBM alterations in SCA1 and trends in SCA3. Based on these data, a Wilcoxon rank sum test will have 95% power to show a difference between controls (mean=0.018, SD=0.019) and SCA (mean= 0.016, SD=0.0019) with 30 subjects per group ($\alpha=0.025$ to take into account the two comparisons of SCA1 and SCA3 versus controls, two-tailed test). Note that this power computation is conservative since the RISCA study included only at-risk subjects, whereas the current study will include both premanifest and early manifest participants. In addition, based on our MRS preliminary data, a Wilcoxon-Mann-Whitney test will have 94% power to show a difference in NAA at baseline between premanifest subjects who have disease onset within the 5 years of the READISCA (conservatively estimated at 1/3 of the participants i.e. $n=7$, mean = 1.2) and those participants who remain in the premanifest stage ($n=14$, mean = 2) for the SCA1 group (standard deviation of 0.4, $\alpha=0.05$, two-tailed test). We will recruit a larger sample size for the SCA3 cohort because: 1) imaging alterations did not reach significance for SCA3 mutation carriers in the RISCA study; 2) the diffusion MRI abnormalities were less pronounced in SCA3 than those in SCA1; and 3) SCA3 is the most common SCA, enabling recruitment of a larger cohort.

Statistical Methods

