For Aim 1 data from the participating centers will include demographics, repeat length (expanded and normal alleles), and scores from the SARA, timed measures, patient-reported outcomes (PRO), and health-related quality of life (QoL) for “core ataxia COA”. Range, scale, and outliers of the combined data will be evaluated. Sex will be considered as a biological variable in all statistical analyses. The cluster structure of combined cross-sectional data will be assessed using a variety of non-linear manifold learning methods to identify similarities and dissimilarities. Association and equality of means will be evaluated using parametric and non-parametric inferential hypothesis testing. Longitudinal analyses for repeated measures will be performed using mixed models and generalized estimating equations (GEE regression). As the drop out processes could differ between cohorts the models will take into account the process (pattern mixture models or joint model if necessary).

Propensity Matching: *Post hoc* group comparative analysis will include propensity matching of SCA1/SCA3 subjects from US and those from Europe which have similar covariate profiles, in order to minimize confounding from covariates. Separate logistic regression runs will be performed to obtain the logit for each subject, where the dependent variable is the group (US cohort vs. European cohort) and covariates are nuisance factors such as gender, age, medical history, etc. Histograms of the fitted logit will be constructed for each group, and subjects will be randomly drawn from the same bins within the two histograms. This approach will be bootstrapped so that repeated sampling of the two groups of subjects with similar confounder profiles can be employed during modeling.

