For Aim 2 centralized data analysis will be performed. De-identified MRI and MRS data will be analyzed in a blind fashion at UMN, as described previously for volumetric, VBM and MRS analyses. Diffusion MRI data will be analyzed using tract-based spatial statistics (TBSS), which is part of the FMRIB’s Software Library (FSL), and tractography to delineate particular white matter (WM) pathways (e.g., cerebellar peduncles). Functional (rs fMRI) data will be pre-processed using FSL, followed by between-group analyses using seed-based connectivity analysis for particular regions of interest, and independent component analysis/dual regression (MELODIC/FIX) for resting-state networks (RSNs). Normative data from the Human Connectome Lifespan project will supplement matched-control data acquired prospectively. Outcome measures will consist of cerebellar and brainstem volumes, gray matter (GM), and WM loss metrics from VBM, metabolite concentrations, fractional anisotropy, mean diffusivity, radial and axial diffusivity, as well as degree of co-activation within RSNs of interest (e.g., motor function). These multi-modal imaging data will then be incorporated in the predictive model to stratify future clinical trial cohorts in Aim 3.

To compare the imaging biomarkers between SCA1, SCA3 and control cohorts, globally and in a pairwise fashion, we will use Wilcoxon rank sum test. In addition, premanifest carriers and early-stage participants will be compared using Wilcoxon rank sum test. Within each SCA group, premanifest and manifest patients will be compared regarding the biomarkers at baseline and during follow-up. If this approach is not conclusive, cluster approaches will be carried out. Sex will be considered as a biological variable to assess potential sex-based differences in imaging results. Finally, the MR biomarkers will be included in the predictive model (Aim 3).

Ethical Conduct of the Study:

This study will be conducted with the highest respect for the individual participants (i.e., subjects) according to the protocol, the ethical principles that have their origin in the Declaration of Helsinki (18th World Medical Assembly, 1964) and its last revision (Fortaleza, October 2013) (48), the ICH Harmonized Tripartite Guideline for GCP and local laws and regulations of the country where the study is performed.

Clinical Trial Registration:

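### Aim 2 names a two-group test for a three-group global comparison, and its group comparisons carry no age or sex adjustment although age may confound them

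*Protocol*

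**What the plan says.** The Aim 2 part of Statistical Methods names one test for all cohort comparisons: "To compare the imaging biomarkers between SCA1, SCA3 and control cohorts, globally and in a pairwise fashion, we will use Wilcoxon rank sum test". It repeats the choice for disease stage: "premanifest carriers and early-stage participants will be compared using Wilcoxon rank sum test". No covariate is attached to either.

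Sex appears separately: "Sex will be considered as a biological variable to assess potential sex-based differences in imaging results". A broader sentence, "Sex will be considered as a biological variable in all statistical analyses", stands in the Aim 1 paragraph. The controls are described as matched, without naming the factors: "Normative data from the Human Connectome Lifespan project will supplement matched-control data acquired prospectively".

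On age, the Aim 2 study population section invites carriers by predicted time to onset, calculated from CAG repeat length and current age. For premanifest and at-risk participants it adds: "we will target an age range of 27-50 years to minimize the probability of including participants too far from disease onset". The Inclusion Criteria table admits early-stage patients at 18-65. If there are fewer than 30 controls, the Summary footnote says: "we will recruit additional asymptomatic subjects who are of either sex aged 18 to 65 with neither SCA1 nor SCA3 mutations".

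**The concern.** There are two separate problems.

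The first is definite. A two-sample test is named for a three-sample question. This is not detail left for an analysis plan, because the protocol fixes a method and that method cannot do the job.

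The second is a risk. Age enters recruitment differently for the groups being compared, and a plain rank sum test attributes any resulting difference to group. If the biomarker varies with age and the mean ages differ, ageing can be reported as disease. Aim 2 is meant to validate markers of premanifest and early disease, so premanifest versus early-stage is a central contrast. The protocol recognises this kind of confounding elsewhere: for US versus European subjects it plans propensity matching on covariates that include gender and age. It states nothing equivalent for the stage comparison.

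**Working it through.** **1. The protocol's own power figure.** Sample Size Justification gives 95% power for the rank sum test with 30 per group, two-tailed alpha 0.025 ("to take into account the two comparisons of SCA1 and SCA3 versus controls, two-tailed test"), and means 0.018 and 0.016. With SD 0.0019 in both groups, the standardised difference is 0.002/0.0019 = 1.05. Simulation gives 94.8%, and t-test power with n multiplied by 3/π gives 95.1%. The 95% therefore reproduces, but only with 0.0019 in both groups. With the control SD as printed (0.019) the power would be about 8%, which is a separate point. SD 0.0019 is used below.

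**2. Cost of a proper global test.** Kruskal-Wallis with 30 SCA1, 40 SCA3 and 30 controls, alpha 0.05, SCA1 mean 0.016 and control mean 0.018:

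| Assumed SCA3 mean | Power |
|---|---|
| 0.016 | 99.0% |
| 0.017 | 95.0% |
| 0.018 | 98.8% |

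Naming the right test needs no larger sample.

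**3. Age, premanifest versus early-stage.** From the Aim 2 study population, n₁ = 20 + 27 = 47 premanifest and n₂ = 10 + 13 = 23 early-stage. Assumptions not in the documents: no disease effect, age SD 8 years in each group, age-biomarker correlation r of 0.2, 0.3 or 0.4, and a given gap in mean age.

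- Shift in biomarker SD units: d = r × gap / 8.
- Approximate noncentrality of the rank sum test: d × √[(47 × 23/70) × 3/π] = d × √(15.44 × 0.955) = 3.84d.
- Rejection rate at two-sided 5%: P(Z > 1.96 − 3.84d) + P(Z < −1.96 − 3.84d).

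Example: r = 0.3 and a 10-year gap give d = 0.375, noncentrality 1.44 and rejection of about 30%.

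| Gap | Formula, r = 0.2/0.3/0.4 | Simulated, r = 0.2/0.3/0.4 |
|---|---|---|
| 0 years | 5/5/5% | about 5% |
| 3 years | 6/7/9% | about 5/7/10% |
| 5 years | 8/11/16% | about 8/11/15% |
| 10 years | 16/30/48% | about 16/28/46% |

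A regression with age as a covariate rejects at about 5% in these scenarios. The 3-year row equals the difference between the window midpoints: (18 + 65)/2 − (27 + 50)/2 = 41.5 − 38.5. That is a reference value, not an estimate of the real gap. With age SD 11 the 10-year row falls to about 10/18/27%.

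**4. Age, one SCA cohort versus controls.** With 30 per group, nominal 2.5%, age SD 8 and r of 0.2, 0.3 or 0.5, the unadjusted test rejects 4.0/5.8/13.4% with a 5-year gap and 6.2/12.7/33.9% with an 8-year gap. With no gap it rejects 2.3-2.4%. A linear model with age and sex rejects 2.0-3.0% (r = 0.3 and 0.5; gaps 0, 5 and 8 years). Its power at the planned effect in those settings is 92-99%.

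**The case against.** The case on the other side has real weight.

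- **The global test is a small slip.** Kruskal-Wallis is the k-sample form of the same rank test, and the sample is ample. This is true, but the sentence is still wrong as it stands.
- **Sex.** A reader might infer that the protocol promises an adjustment that its test cannot deliver. It does not. The Aim 2 text promises only to assess sex-based differences, which a comparison of men with women or a sex-stratified rank test would meet. The wider sentence belongs to Aim 1.
- **Age by design.** A reader might infer that the groups are bound to differ in age. The documents give eligibility windows, not mean ages. The windows overlap, and the early-stage window also reaches below 27. Premanifest carriers and at-risk participants, the main source of controls, share the 27-50 target. Inviting carriers within 10 years of predicted onset probably narrows the gap to early-stage patients. The 18-65 top-up controls are recruited only if needed.
- **Matching.** It would be wrong to say that no matching is planned. Controls are called matched, and the factors could be set out in a plan not shown. The wording does not reach premanifest versus early-stage.
- **Downstream harm.** A reader might infer that false positives pass into the Aim 3 predictive model as validated markers. The text feeds the imaging data into that model and makes rank sum significance no condition of entry. Aim 3 already plans mixed and joint mixed models for MR biomarkers.
- **Scanner and head size.** One scanner model and one head coil are specified at all six sites, with harmonised protocols. Volumetric methods follow earlier descriptions that may already handle head size.
- **Over-adjustment.** In carriers chosen on age and CAG length, age tracks disease stage, so adjustment may remove real signal.

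The last point and the uncertainty about the age gap both stand. They limit the claim but do not restore the global test, and they do not justify an unadjusted comparison as the only stated analysis.

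**Conclusion.** The concern holds in two parts of different strength. The named global test is wrong as written, with no assumption needed. The absence of age and sex adjustment from the pairwise and stage comparisons is a stated method that leaves them open to confounding by age, most clearly for premanifest versus early-stage. For comparisons with controls the risk depends on matching factors that are not named.

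The size cannot be derived from the protocol. With no age gap there is no inflation. Under the assumptions above it runs from about 5-10% (3 years) to 16-46% (10 years) at a nominal 5%. The upper figures illustrate the risk and do not predict it. This should be corrected before analysis, but it does not show that any Aim 2 result will be false.

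**What to change.** 1. Name a three-group global test: Kruskal-Wallis, or the 2-df group test in a regression.
2. Make the main comparisons a regression of each biomarker on group (on ranks if skewed), adjusted for age and sex. Take pairwise contrasts from that model. Add site and, for volumes, head size where group sizes allow.
3. Keep the unadjusted Wilcoxon and Kruskal-Wallis tests as sensitivity analyses, and report adjusted and unadjusted results side by side, because age tracks stage in carriers.
4. State the factors on which controls are matched.

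The cost is wording and some degrees of freedom. The covariates are already collected or can be derived from the scans. The full set (group, age, sex, five site terms, head size) is 9 coefficients plus an intercept. That leaves 70 − 10 = 60 residual degrees of freedom for the pooled stage comparison, but only 30 − 10 = 20 within SCA1 (20 versus 10). There, age and sex alone are more realistic.

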Appendix – READISCA Telephone Screen

Have you ever been screened or completed any research studies for spinocerebellar ataxia?  Yes  No If “YES” – Are you currently receiving treatment from the research study?  Yes  No If “YES” schedule screen three months after completion of interventional study.			
Are you looking to participate in READISCA Clinical Trial Readiness for SCA1 and SCA3?  Yes  No If “YES” please explain the study to the potential participant verbally, providing all pertinent information (purpose, procedures, risks, benefits, alternatives to participation), and allow the potential participant ample opportunity to ask questions. If participant agrees, send ICF to participant.			
Are you experiencing symptoms of spinocerebellar ataxia?  Yes  No Do you or family member of yours have a genetic diagnosis of SCA1 or SCA3?  Yes  No If necessary, are you willing to undergo video screening assessment?*  Yes  No Are you willing to participate in MRI/MRS sub study?  Yes  No If “YES” complete the MRI Questions checklist below *Offered to potential participants from remote areas. Contact information should be provided to HMRICC as soon as signed Informed consent form is received from participant			
How did you hear about us?  NAF  CoRDS  Clinicaltrials.gov  Flyer  Friend  Web  Other			
Age:	Gender:  M  F	If female: Pregnant or nursing?  Yes  No	
Do you currently receive any of the following therapies? Or Have you ever used the following in the past?		If “YES” – How often do you currently use? Or How often did you use in the past?	
 Physical Therapy  Speech Therapy  Occupational Therapy  Psychotherapy  Inpatient Rehabilitation		_____x per week/month/past* _____x per week/month/past _____x per week/month/past _____x per week/month/past _____x per week/month/past _____x per week/month/past *Must have no changes in physical/occupational therapy status for 2 months prior to enrollment	
MRI/MRS Questions Prescreen Checklist: Do you have any metal in your body?  Yes**  No If “YES” , get more details and include comment below Are you claustrophobic or have difficulty in enclosed areas?  Yes**  No If “YES” , exclude. Have you ever lost consciousness?  Yes**  No If “YES” , for how long? If LOC >10 mins, exclude. Have you ever worked with metals (welder, electrician, etc.)?  Yes**  No If “YES” , did you wear safety glasses? If no, exclude. Do you weigh over 300lbs  Yes**  No If “YES” , exclude.			
Do you know anyone else who may qualify for the study?  Yes  No If “YES” Are you willing to contact the person(s) and ask them to contact us?  Yes  No If “YES” please provide site phone and email contact.	Meets AIM 2 eligibility criteria?  YES  No** (why not?) HMRICC contacted?  Yes** Date:  No** (why not?)	List of Potentially Prohibitive Metals Pacemaker  Yes  No Stimulator  Yes  No Infusion pump  Yes  No Insulin pump  Yes  No Prosthesis  Yes  No Metal joints  Yes  No Ear implants  Yes  No Vascular clips  Yes  No Tattoo  Yes  No Hearing aid  Yes  No Permanent make-up  Yes  No	_____ First name, Last initial _____ Phone # (and/or E-mail) Personal #?  Yes  No Phone screen completed by: _____ Date:
Mailing Address:
